(OAB), a condition characterized by urgency to urinate.¹ Overactive bladder is commonly associated with urgency urinary incontinence (UUI), and older adults with UUI are at twofold higher risk for falls. UUI is increasingly being recognized as a marker for musculoskeletal weakness.^{2, 3} According to the bio-psycho-ecological paradigm,^{4, 5} falls associated with overactive bladder are a combined result of the interaction between three elements: bladder urgency; mental abilities including anxiety and embarrassment related to bladder urgency; and physical difficulty in reaching the toilet in a timely fashion. Anti-muscarinic medications are the most common class of medication used for the treatment of UUI. Six main anti-muscarinic medications are available in the United States, with similar efficacy (Qaseem 2014, AUA/SUFU OAB guidelines), and are generally prescribed based on insurance coverage as well as tolerance of side effect profile. These medications are known to improve at least two of these domains: bladder urgency,⁶ and mental anxiety related to urinary incontinence.⁷ Prior studies also suggest that reduction of bladder urgency with medications may improve ability to reach the toilet by improving physical ability, which is the third domain associated with falls. In an abstract presented at AUGS 2014, we have shown that treatment of overactive bladder in adults (mean age 61.0 ± 13.8) with fesoterodine was associated with improved physical activity as measured by the two physical activity questions of the SF-12.⁸ Several studies have reported that treatment of overactive bladder is associated with improvement in physical activity related to travel, transportation, and planning to locate restrooms.^{9, 10, 11} While these activities do not necessarily correlate with physical activities known to reduce the risk of falls e.g. walking, climbing stairs, or participating in sports these studies provide promising evidence that treatment of OAB with anti-cholinergic medications could potentially reduce falls. However, though several physical activity questionnaires exist, none have been validated in older adults with urgency urinary incontinence. Finally, anti-cholinergic medications have been implicated in neurocognitive changes that could potentially increase the risk of falls.¹² Therefore, there remains a key gap in knowledge regarding the effect of anti-cholinergic medications on physical activity and neurocognitive testing in older adults with urgency urinary incontinence. The efficacy of medications is closely related to adherence. Despite multiple benefits from anti-cholinergic treatment, the estimated adherence to anti-cholinergic medication is less than 10% at one year.¹³ Poor adherence carries the potential for wasted health care resources and continued suffering for patients. There is a lack of knowledge on how to best identify patients who will be adherent to anti-cholinergic treatment, and therefore derive the most benefit from medication. Recent studies in other conditions such as depression suggest that a key indicator for adherence is patient-expressed preference for treatment. We have previously shown that the health belief model is valid in women with OAB; women who believe in the intrinsic harm of medications have significantly worse adherence than those who believe in the benefit of medications.¹⁴ Urgency urinary incontinence is associated with increased risk of falls in older adults: Falls in the elderly have severe life-threatening consequences including injuries, immobility, and mortality.¹⁵ Several systematic reviews have confirmed that urgency urinary incontinence is an independent risk factor for falls.^{16, 17, 18} Gosch et al found that amongst patients admitted for fragility fractures, those with urinary incontinence displayed increased rates of cognitive dysfunction and depression compared to those without incontinence. Patients with incontinence were more likely to have musculoskeletal complaints that inhibit mobility, including lower back pain, weaker grip strength, and slower walking velocity.² Despite the close relationship between UUI and falls, studies that determine if treatment of UUI can reduce fall risk are lacking. Improvement in physical activity can reduce the risk of falls in older adults: Women with UUI exhibit avoidance of physical exercise.^{20, 21, 22} One of the major risk factors for falls is decline in physical functioning, which is accelerated by lack of physical activity. In a meta-analysis of 30 studies, decline in lower extremity strength was associated with falls (odds ratio 1.76, 95% CI 1.3-2.4).²³ On the other hand, improvement in physical activity by strength and balance training or simply by increased physical activity is effective in reducing fear of falling as well as actual falls.^{24, 25} The Nurses Health Study prospectively showed that older women who remained physically active longer were less likely to report the development of new onset UUI.²⁶ However, it is not known if treatment of UUI can improve physical activity in older adults. Anti-cholinergic medications may improve physical activity in older adults with urgency urinary incontinence: Prior studies suggest that treatment of overactive bladder with anti-cholinergic medications is associated with improvement in physical activity associated with quality of life.^{9, 10, 27, 28} In these studies, activity was measured using the Physical Limitations domain of the Kings Health Questionnaire (KHQ) or the Coping score of the Overactive Bladder Questionnaire (OAB-q). However, these domains examine social-related activities such as planning for travel/transportation and locating of convenient restrooms, and are therefore quality-of-life rather than physical activity measures. This may not reflect change in actual physical activity such as walking, climbing stairs, or participating in sports. Data from our preliminary study at Penn presented at AUGS/IUGA 2014 suggest that treatment with fesoterodine, in combination with behavior modification and Kegel exercises, improves women's

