(Tzefos 2009, AHRP reference guide) Additionally, fesoterodine has been compared to tolterodine, and may show greater efficacy. (Tzefos 2009) In fact, fesoterodine tends to have low incidence of dry mouth, and moderate incidence of constipation compared to other anti-muscarinics, making it a well-tolerated and appropriate first choice for most patients.(Ellsworth 2014) Low CNS penetration may also potentiate fewer CNS side effects.(Ellsworth2014) Additionally, our previously presented data on the potential positive effects of anticholinergic medication on physical activity was collected using fesoterodine, so there is a precedent for using this anticholinergic in a study examining changes in activity and sedentary behavior. Therefore, fesoterodine, the drug used in this study, is an appropriate medication for routine and standard care of overactive bladder. Fesoterodine is being supplied by Pfizer for the use of this study. As part of routine clinical care at the urogynecology clinics of the University of Pennsylvania Health System, all patients receive a pelvic exam, measurement of post-void residual by bladder ultrasound, and administration of four urinary questionnaires as part of evaluation of urinary symptoms. The OABq-SF and the UDI-6 will be used to screen patients. Inclusion Criteria: adults aged 65 or older, urinary urgency of quite a bit severity or more on the Overactive Bladder Questionnaire-Short Form (OABq-SF),50 who are eligible for pharmacologic therapy for overactive bladder Exclusion Criteria: predominant stress incontinence (on UDI-6), current/recent use (6 m) or contraindication to anti-cholinergic medication, severe voiding difficulties, men on 5-alpha reductase inhibitors, severe neurologic disease, recent anti-incontinence or prolapse surgery, other urinary tract conditions such as calculus or recurrent UTI. Recruitment/Retention Experience: The urogynecology/urology clinics of the Hospital of University of Pennsylvania are high volume referral clinics staffed by four urogynecologists and one urologist. We see 125 female and 50 male patients with OAB per month with eligibility:participation ratio of 1.5:1 in clinical trials.42, 48, 51 In recent trials, 50% of recruited adults were Caucasian and 45% African-American. We anticipate that the female:male ratio will be 2:1. Recruitment : Pre-screening will occur at a patients routine visit, or via chart review following clinical care. If a patient appears to be eligible, they will be referred to the study coordinator to schedule a baseline visit. Patients of urogynecology or other referring geriatrics/urology/primary care practices may also self-refer for participation, as long as their medical records are available for eligibility determination. Baseline visit: At this visit, the trained coordinator will obtain informed consent, administer physical activity and other questionnaires (see Instrument and Testing Schedule below). Routine pre-treatment counseling on medical treatment, as well as counseling on additional non-medical (biofeedback, behavioral strategies, pelvic floor muscle training) and interventional treatments (neuromodulation), will also be provided. Then the coordinator will administer the Preference instrument on a bidirectional scale with 0 being undecided, and either extreme (5 or -5) being a strong preference for that particular treatment. The Short Physical Performance Battery (SPPB) test will also be performed with the oversight of trained personnel for safety. Accelerometers and instructions for wearing the accelerometer will be provided at that time. The monitor will be retrieved from the patient by a study coordinator or investigator 1 week later. Intervention: All subjects (irrespective of preference) will receive a 90-day supply of open label fesoterodine 4 mg per day. They will start medication 1 week after the baseline visit. After 4 weeks of treatment, dose may be increased to 8 mg over the telephone based on symptom report. This dosing regimen is direct alignment with clinical care. Change of prescription to another anti-cholinergic may occur during the study period, if determined necessary by the physician. Criteria that would warrant stopping fesoterodine include: - inability to tolerate common side effects, including dry mouth, dry eyes, and constipation - lack of satisfactory urinary symptom control on the highest dose of fesoterodine - immediate withdrawal in case of life-threatening side effects (uncommon, including angina, angioedema, diverticulitis, gastroenteritis, heat prostration, hypersensitivity reactions, irritable bowel syndrome, QT prolongation) Once withdrawn from fesoterodine, managing physicians would use their clinical judgment to switch the patient to another anti-cholinergic medication or switch to another class of medication (beta 3 agonist, or mirabegron). These patients would continue to be followed until after the 8 week follow-up visit, as the statistical plan will involve intention-to-treat analysis. The patients will continue to participate in the 8 week follow-up visit (including questionnaires and SPPB), regardless of whether or not they were switched to another medication. All adults will receive printed educational material on fluid modification, behavioral strategies, and Kegel exercises. 8 week follow up visit: One week prior, the study coordinator will once again provide subjects with accelerometers and instructions for wearing the accelerometer. At the 8 week visit, the patient will again complete self-administered physical activity, urinary symptoms, adherence, pill count, and neurocognitive instruments and tests with the oversight of a trained investigator (see Instrument and Testing Schedule below). The monitor will be retrieved from the patient by a study coordinator or investigator at the 8 week follow up visit. Instrument and Testing Schedule BASELINE VISIT: Urinary questionnaires (OABq-SF, UDI-6) Preference: Belief in Medication Questionnaire (BMQ), Bidirectional Visual Analogue Preference scale Physical activity:

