
Characteristics of the Study Population

Target population

Adult subjects aged 65 or older with overactive bladder undergoing treatment with medication

Subjects enrolled by Penn Researchers

80

Subjects enrolled by Collaborating Researchers

0

Accrual

Recruitment/Retention Experience: The urogynecology/urology clinics of the Hospital of University of Pennsylvania are high volume referral clinics staffed by four urogynecologists and one urologist. We see 125 female and 50 male patients with OAB per month with eligibility:participation ratio of 1.5:1 in clinical trials. In recent trials, 50% of recruited adults were Caucasian and 45% African-American. We anticipate that the female:male ratio will be 2:1. Sample Size: Specific Aim 1: A sample size of 68 evaluable subjects will provide 90% power to detect a correlation coefficient of 0.72 or greater, assuming a correlation coefficient of 0.5 or less between the physical activity questionnaires and the criterion standard (accelerometer) is undesirable (null hypothesis). Assuming a 15% loss to follow-up, we plan to enroll 80 patients to ensure an adequate sample of at least 68 subjects with complete datasets. Specific Aim 2: We have conservatively assumed that 50% subjects will express preference for medication. Prior Penn studies show 56% adherence at 8 weeks in unselected subjects. Assuming that adherence will be 80% in subjects expressing preference for medication, a sample size of 80 subjects will provide 90% power to demonstrate a 30% difference in adherence rates in subjects who do or do not have preference for medication. Specific Aim 3: Assuming two-tailed alpha of 0.05, a sample size of 80 subjects will provide 90% power to show a 30% difference in physical activity in the proportion of subjects expressing preference for medication versus those without preference.

Key inclusion criteria

Inclusion Criteria: adults aged 65 or older, urinary urgency of quite a bit severity or more on the Overactive Bladder Questionnaire-Short Form (OABq-SF),⁵⁰ who are eligible for pharmacologic therapy for overactive bladder

Key exclusion criteria

Exclusion Criteria: predominant stress incontinence (on UDI-6), current/recent use (6 m) or contraindication to anti-cholinergic medication, severe voiding difficulties, men on 5-alpha reductase inhibitors, severe neurologic disease, recent anti-incontinence or prolapse surgery, other urinary tract conditions such as calculus or recurrent UTI.

Vulnerable Populations

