risk), Short Physical Performance Battery Urinary: Questionnaires (OABq-SF, UDI-6) Bowels: Questionnaires (Birmingham) Quality of Life: SF-12 Adherence: Questionnaires (BMQ follow up, MASRI), pill count Patient Global Index of Improvement (PGI-I) form The study coordinator will again provide subjects with accelerometers and instructions for wearing the accelerometer, one week prior to the 8 week visit. The monitor will be retrieved from the patient by a study coordinator or investigator at the 8 week visit. Instrument and Testing Schedule BASELINE VISIT: Preference: Belief in Medication Questionnaire (BMQ, gold standard), Bidirectional Visual Analogue Preference scale Physical activity: Accelerometer (gold standard), Self-reported questionnaires (IPAQ, CHAMPS) Neurocognitive measures: Questionnaires (Mini cog, Falls risk), Short Physical Performance Testing Urinary: Questionnaires (OABq-SF, UDI-6) Quality of Life: SF-12 Bowels: Questionnaires (Birmingham) 8 WEEK FOLLOW-UP VISIT: Physical activity: Accelerometer (gold standard), Self-reported questionnaires (IPAQ, CHAMPS) Neurocognitive measures: Questionnaires (Mini Cog, Falls risk), Short Physical Performance Testing Urinary: Questionnaires (OABq-SF, UDI-6) Bowels: Questionnaires (Birmingham) Quality of Life: SF-12 Adherence: Questionnaires (BMQ follow up, MASRI), pill count Patient Global Index of Improvement (PGI-I) form

The following documents are currently attached to this item:

There are no documents attached for this item.

Deception

Does your project use deception?

No

International Research

Are you conducting research outside of the United States?

No

Analysis Plan

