Analysis Plan Specific Aim 1 and 2: We will evaluate physical activity, adherence, and neurocognitive function before and after treatment to examine changes from baseline to 8 weeks in subjects with and without preference for medication. Concurrent validity, the relationship of the instrument to other similar evaluations, will be measured by comparing IPAQ, and CHAMPS scores to accelerometer data at baseline using the Spearman correlation coefficient and the intraclass correlation coefficient. Specifically, we will compare energy expenditure in MET*min/week (IPAQ) or MET*hour/week (CHAMPS) to that measured by the Actigraph accelerometer over the course of a week. For preference, we will compare subjects scores as indicated on the bidirectional scale to their necessity-harm differential as calculated by the Belief Screen of the BMQ using Spearman correlation coefficient. Contingency analyses tables will be used to determine the sensitivity and specificity of the bidirectional preference scale and the necessity-harm differential (as calculated on the Belief Screen) that best discriminates between those with preference for medication and those without. Discriminant validity, the ability to distinguish between populations, will be determined by comparing mean differences in energy expenditure for each physical activity instrument between responders and non-responders to anticholinergic medication as defined by the PGI-I. We will compare total MET*min/week (IPAQ) or MET*hour/week (CHAMPS), as well as energy spent in sedentary and moderate-to-vigorous physical activities (CHAMPS) between responders and non-responders using Wilcoxon rank sum test. For preference, we will compare the BMQ Belief necessity-harm differential and bidirectional preference scale score using Wilcoxon rank sum test. Responsiveness, the ability of the instruments to detect clinically meaningful change, will be assessed. First, pretreatment energy expenditure and preference will be compared with post-treatment activity and preference scores, respectively, using the t-test. Next, effect size (change in mean score/SD of baseline) and standardized response mean (change in mean score/SD of the change) will be assessed. For both, values of 0.50.7 will be considered moderate responsiveness; 0.81, good; and 1, excellent. We will measure minimum clinically important difference (MCID); specifically, the smallest change in physical activity associated with clinically meaningful change in global rating scale (mean change in energy expenditure in subjects indicating a little better or greater in the global rating scale). Specific Aim 3: We will compare within subject change in physical activity from baseline to 8 weeks using the paired t-test. Improvement in physical activity will be defined as 15% increase in energy expenditure as compared to baseline. The effect of age, comorbidities, baseline activity, severity of cognitive impairment, BMI on physical activity will be examined using regression analysis. We will also compare change in activity, proportion of subjects

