
showing improvement in activity, adherence (80% or greater, as measured by pill count and MASRI), response to medication (PGI-I), overall quality of life (SF-12), neurocognitive and balance function (MMSE and Berg Balance Scale scores, respectively), and urinary symptoms (OABq-SF score) in adults expressing preference for medication to those expressing no preference. The effect of preference will be measured using regression analysis, with adjustment for baseline physical activity, Charlson co-morbidity index, age, and BMI.

The following documents are currently attached to this item:

There are no documents attached for this item.

Data confidentiality

- Paper-based records will be kept in a secure location and only be accessible to personnel involved in the study.
- Computer-based files will only be made available to personnel involved in the study through the use of access privileges and passwords.

Prior to access to any study-related information, personnel will be required to sign statements agreeing to protect the security and confidentiality of identifiable information.

- Wherever feasible, identifiers will be removed from study-related information.

A Certificate of Confidentiality will be obtained, because the research could place the subject at risk of criminal or civil liability or cause damage to the subject's financial standing, employability, or liability.

A waiver of documentation of consent is being requested, because the only link between the subject and the study would be the consent document and the primary risk is a breach of confidentiality. (This is not an option for FDA-regulated research.)

Precautions are in place to ensure the data is secure by using passwords and encryption, because the research involves web-based surveys.

Audio and/or video recordings will be transcribed and then destroyed to eliminate audible identification of subjects.

Subject Confidentiality

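### The Aim 3 preference regression leaves out baseline cognition and urgency severity, both collected, so residual confounding could be credited to preference

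*Combined protocol and SAP*

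**What the plan says.** The Specific Aim 3 part of the Analysis Plan contains two regression statements.

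- The first concerns predictors of activity: "The effect of age, comorbidities, baseline activity, severity of cognitive impairment, BMI on physical activity will be examined using regression analysis".
- The second concerns preference: "The effect of preference will be measured using regression analysis, with adjustment for baseline physical activity, Charlson co-morbidity index, age, and BMI". It follows a list of outcomes that includes change in activity, the proportion improving and adherence.

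No other section adds covariates to the second model.

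Both omitted variables are measured before treatment. The Instrument and Testing Schedule under Procedures lists, for the baseline visit, "Neurocognitive measures: Questionnaires (Mini cog, Falls risk), Short Physical Performance Testing Urinary: Questionnaires (OABq-SF, UDI-6".

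On urgency, the Background says: "Prior studies also suggest that reduction of bladder urgency with medications may improve ability to reach the toilet by improving physical ability". The Design section gives, among the reasons for stopping the drug, "lack of satisfactory urinary symptom control on the highest dose of fesoterodine". Baseline OABq-SF is a covariate in no model in the Analysis Plan.

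The Design section describes a prospective cohort in which every subject receives fesoterodine whatever preference they state.

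**The concern.** Preference is a characteristic that subjects bring with them, so the groups being compared may differ in other ways. Adjustment is the only device the plan has for separating preference from those differences.

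The plan is not consistent about cognition. Its activity regression names five factors. The preference regression keeps four of them, with comorbidity made specific as the Charlson index, and drops only cognition, without giving a reason. A factor thought to act on activity is a natural candidate for the model that estimates the effect of a non-randomised exposure on activity.

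Urgency severity is a plausible second candidate. It could influence who wants a drug, who keeps taking it and how far activity can change. That is a judgement, not something the documents state.

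At stake is the Aim 3 claim about the impact of preference. If either variable differs between the preference groups and also acts on the outcome, part of its effect would be reported as an effect of preference, or would mask one.

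**Working it through.** **1. The two covariate lists side by side**

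| Factor | Activity regression | Preference regression |
|---|---|---|
| Age | yes | yes |
| Comorbidity | yes | yes (Charlson) |
| Baseline activity | yes | yes |
| BMI | yes | yes |
| Cognitive impairment | yes | no |
| Baseline urgency (OABq-SF) | no | no |

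**2. Group size**

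The plan gives no figure for confounding, so the only planned figure to reproduce is the evaluable sample. The Accrual section enrols 80 and allows 15% loss: 80 × 0.85 = 68, as stated. The same section assumes that 50% prefer medication, giving 34 per group.

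**3. Illustrative size for a continuous activity outcome**

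The documents give no association of urgency or cognition with preference, so both inputs below are assumptions:

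- gap between preference groups in the omitted variable: 0.3 or 0.5 SD;
- standardised effect of that variable on the outcome, beyond the four planned covariates: 0.3 or 0.4.

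Bias = gap × effect. Noncentrality = bias / √(2/34), where √(2/34) = 0.2425. The true error rate of a two-sided 5% test is Φ(nc − 1.96) + Φ(−nc − 1.96).

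| Gap | Effect | Bias (SD) | Noncentrality | True error rate |
|---|---|---|---|---|
| 0 | any | 0 | 0 | 5.0% |
| 0.3 | 0.3 | 0.09 | 0.37 | 6.6% |
| 0.3 | 0.4 | 0.12 | 0.49 | 7.8% |
| 0.5 | 0.3 | 0.15 | 0.62 | 9.5% |
| 0.5 | 0.4 | 0.20 | 0.82 | 13.1% |

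**4. Illustrative size for adherence**

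Suppose that a binary confounder differs by 0 to 30 points between the groups and shifts adherence by 10 to 30 points (again assumptions). The bias is then 0 to 0.30 × 0.30 = 9 points, against the 30-point difference the plan is sized for. At the plan's 56% overall adherence and 34 per group, the exact rejection rate of the two-sided test of proportions rises from 4.9% with no bias to 11.3% at 9 points.

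**5. Cost of the extra terms**

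- Linear model, 68 subjects: preference plus four covariates leaves 68 − 1 − 5 = 62 residual degrees of freedom. Two more terms leave 60.
- Adherence model: at 80% and 50% adherence in 34 + 34, the non-adherent number 34 × 0.20 + 34 × 0.50 = 23.8, about 24. At 56% overall they number 68 × 0.44 = 29.9, about 30. Seven terms give 24/7 = 3.4 to 30/7 = 4.3 events per parameter. The planned five terms already give only 24/5 = 4.8 to 30/5 = 6.0.

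**The case against.** The strongest reply is that confounding needs a link to preference, and no section supplies one for urgency or cognition. What the Background ties to adherence is mainly beliefs about medicines, satisfaction and shared decisions. This stands: the bias cannot be shown to exist, only not excluded.

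A reader might infer that the plan itself treats both variables as drivers of activity and adherence, so that confounding is certain. The documents do not go that far. The Analysis Plan names cognition only, and for activity only. The Background passage on urgency concerns reducing it with treatment, not its baseline level. For adherence, the nearest statements are poor symptom control as a stopping criterion and a general reference to clinical factors.

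A reader might also extend the point to Aim 2. That aim asks whether a preference instrument is valid, judged by whether those who prefer medication adhere more. A score can predict adherence whatever lies behind it, so the criticism does not carry over.

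The design also narrows both variables. Entry requires "urinary urgency of quite a bit severity or more on the Overactive Bladder Questionnaire-Short Form (OABq-SF", severe neurologic disease is excluded and subjects must be competent to consent. Baseline activity, already in the model, may absorb part of any urgency effect. These limits reduce the room for imbalance but do not remove it.

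Finally, the adherence model cannot carry many terms. That is correct, and it changes the remedy for that outcome.

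**Conclusion.** The point holds as a gap in prespecification. The preference model omits two collected baseline measures, one of which the plan lists as a factor for physical activity alongside the same four covariates. Residual confounding could therefore be credited to preference in Aim 3.

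Its size and direction are unknown. The 6.6% to 13% error rates rest wholly on the assumed gaps and effects, on an even split of 68 subjects, and on a simple two-group comparison in which the effect is what remains after the planned covariates. With no gap the rate stays at 5%. Even the largest adherence bias tried, 9 points, would not by itself account for a 30-point difference. The change is worth making because it is cheap, not because bias has been demonstrated.

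**What to change.** In the Specific Aim 3 text of the Analysis Plan:

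- **Physical activity models.** Add baseline OABq-SF score and baseline Mini-Cog to the covariate list, and report the preference estimate with and without them. Name the Mini-Cog explicitly: the Aim 3 text refers to the MMSE, which is not on the visit schedule.
- **Adherence.** Keep the planned covariates for the main model and prespecify the two additions as a sensitivity analysis. Use a penalised logistic fit (for example Firth) and state how the preference term is handled in it.
- **Reporting.** Show baseline OABq-SF and Mini-Cog by preference group, so that readers can see whether there is an imbalance to adjust for.

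The cost is a wording change to the plan with no new data collection: two parameters and slightly less precision in the activity models, and a second estimator to specify for adherence.
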